5.2 Secondary Outcomes

- 5.2.1 Since the first secondary objective is to examine metabolic and microbial signatures are two time points (pre- and post- surgery) therefore the following outcomes will be gathered to examine this:
 - 5.2.1.1 Quantitative assessments of metabolic characteristics measured at pre-surgery
 - 5.2.1.2 Quantitative assessments of microbial assessments measured at pre-surgery
 - 5.2.1.3 Quantitative assessments of metabolic characteristics measured at post-surgery
 - 5.2.1.4 Quantitative assessments of microbial assessments measured at post-surgeryUsing these four sets of quantitative assessments, “signatures” will be developed (described in statistical analysis section) and compared to see whether there are characteristics that remain similar or change when comparing pre- and post-surgical measures.
- 5.2.2 Patient LC Stage will be gathered as a secondary outcome. This outcome will be used with the outcome measures gathered for primary outcome 5.1.2 (described above) to address the secondary objective (To identify signatures which are associated with LC stage).
- 5.2.3 Patient pulmonary function status (assessed by [name]) will be gathered as a secondary outcome. This outcome will be used with the outcome measures gathered for primary outcome 5.1.2 (described above) to address the secondary objective (To identify signatures which are impacted by patient’s pulmonary function status).

6.0 Analytic Plan

6.1 Sample Size and Power

This is a pilot study therefore; many of the objectives are exploratory in nature. With this in mind, we plan to recruit two cohorts of patients with this study, 45 female and 45 males. In order to be able to examine the questions concerning the possible relationships of metabolic and microbial signatures over time and with lung cancer outcomes, both pre- and post- surgery measures are needed. Therefore, each patient must provide both a pre- and post-surgery sample (optional blood will be allowed) in order to be used in the signature analyses. If a post collection is not performed or collection is unsatisfactory, the patient will be replaced. Therefore, our target sample size of 90 patients (45 male/45 female) is the target for patients with both pre- and post- samples collected.

Pilot Study: Metabolic and microbial profiling of lung cancer
Wake Forest Baptist Comprehensive Cancer Center (WFBCCC)
WFBCCC # 03219

First, for the primary objective of assessing feasibility, we can determine the total number of patients needed in order to enroll 90 patients. To examine this question we will determine 1) the number of patients screened for the trial, 2) among those screened, the number who are eligible, 3) among those eligible, the number who consent to participate, 4) among those who participate, the number who provide pre-surgery samples, and 5) among those who provide pre-surgery samples, the number who provide post-surgery samples. Based on our design we will enroll patients until 90 provide pre- and post- surgery samples.

Since we do not know prospectively how many patients will be needed to enroll 90 we will conservatively estimate several possible scenarios and for each scenario describe the width of the corresponding 95% Exact Clopper Pearson confidence interval for proportions.

The table below shows different total number of patients needed to enroll 90 for the study, beginning with 120 (75% enrollment rate) to 180 (50% enrollment rate).

# screened and eligible	Number enrolled	Enrollment rate	Lower 95% limit	Upper 95% limit
120	90	75%	0.66	0.82
150	90	60%	0.52	0.68
180	90	50%	0.42	0.58

As can be seen from the above, the confidence intervals for each scenario are approximately +/- 10% or less depending on the scenario observed.

For the other primary outcomes, metabolic and microbial assessments taken at two time points (pre- and post- surgery), we can determine statistical power in several ways. One straight-forward approach will be to assess the difference in biomarkers (metabolic or microbial) that can be detected when comparing pre- and post- surgical assessments within patients. If there are 90 patients then there is 80% power (using an alpha=0.05, 2-sided) to detect a difference in a biomarker measure equal to 0.30 standard deviations for that marker.

Since this is a pilot study, the above power calculations suggest that useful data concerning feasibility and effect size assessments for biomarkers can be determined in this study. Multiple comparison adjustments are not considered at this time since the focus of examining these effect size estimates is to determine an overall ranking of measures, in order to inform future studies concerning which signatures may be most promising to examine further.

6.2 Analysis of Primary Outcome

To examine the questions of feasibility, we will generate a series of estimates of proportions for each question (i.e. proportion of screened who are eligible, etc.). Next, we will estimate 95% exact Clopper-Pearson confidence intervals for each feasibility estimate.

6.3 Analysis of Secondary Outcomes

For the analysis of metabolic and microbial measures we will examine each marker assessed both at pre- and post- surgery. We hypothesize that markers that are associated with lung cancer will change between the pre- and post- surgery setting, whereas markers that are independent of lung cancer will not change between the two time points. Therefore, a first analysis will be to examine

Pilot Study: Metabolic and microbial profiling of lung cancer
Wake Forest Baptist Comprehensive Cancer Center (WFBCCC)
WFBCCC # 03219

a series of paired t-tests to determine which markers significantly change between the two time points for patients.

In addition to this analysis, we wish to determine whether there are any marker signatures that appear in groups of patients. To do this we will use cluster analysis methods to determine whether there are any groups of patients who share similar marker profiles pre-, post- or change from pre- to post- for metabolic and microbial measures. If we are able to identify clusters of patients with common marker signatures, we will then determine whether there are other disease characteristics that are shared by these patients (i.e., tumor stage, lung function, etc.). This analysis approach will also be used below to address the analysis of secondary outcomes. As stated above, this is a pilot study, therefore these cluster analyses will be considered exploratory and hypothesis generating.

To address the two secondary objectives, we will use the same data gathered for the primary objective as described above, however we will compare those data to the two secondary outcomes measures (LC Stage and patient pulmonary function). The analytic difference between these two measures is that LC stage will be an ordinal variable and pulmonary function is a continuous measure.

For LC Stage, we will examine whether pre-surgery, post-surgery or change from pre- to post-surgery metabolic or microbial measures are different depending on LC Stage. To do this we can consider the metabolic or microbial measures as outcomes and use a general linear models framework to see if LC Stage (included as a class variable, but then examined as an ordinal variable using a contrast statement in GLM) is associated with any marker.

In addition to this analysis where individual markers are considered separately, we will use cluster analyses (as described above) based on the marker data and then determine whether there are associations between cluster membership and LC Stage using 2-way contingency tables.

For pulmonary function, we will use the same approach as for LC Stage, except that pulmonary function will be considered as a continuous variable in the model. Thus, we can examine associations (correlations) between the marker measures and pulmonary function. In addition, pulmonary function can be examined at both time-points (pre- and post- surgery) thus we can examine the relationships between pulmonary function measures and biomarker measures at each time points (and the change in measures over time).

In addition to these analyses, additional exploratory analyses will be examined to determine whether other patient level characteristics (i.e., gender, age, smoking history (current/former/never), etc.) are associated with different metabolic and/or microbial signatures or measures in a general linear model framework.

Since this is a pilot study and the sample size is moderate ($n=90$), these additional analyses will be primarily hypothesis generating to allow us to determine whether there are potential signals in the data that may need to be further examined in larger trials.

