2.2 Secondary Objective

2.2.1 To identify and assess metabolic and microbial signatures collected at pre- and post-surgery and determine which are indicative of LC.

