Biofluid and tissue metabolomic analysis: Saliva, serum, urine and tissue aliquots will be prepared for analysis by standard processing according to published methodology(5); (19). Two platforms of unbiased metabolomics analysis will be completed using both a Q Exactive GC system and a Q Exactive LC system. Utilizing two chromatographic methodologies will maximize our metabolite identification coverage. The collected spectra will be processed using Thermo Scientific™ TraceFinder™ 4.1 software. The initial data processing will include baseline correction, peak deconvolution, retention index, signal to noise ratio calculation, unique mass detection, peak area determination, and compound identification based on the spectral pattern similarity match against established mass spectral reference libraries (NIST14, National Institute of Standard Technology, NIH and a high-resolution mass spectral library from TraceFinder™ software). Identified spectral matches will be identified for pre- and post-surgery following metabolomics standards initiative (MSI) guidelines for metabolite identification (Level 2), with a match score requirement of equal to or greater than 80%. Aligned metabolomic data analysis software, MetaboAnalyst 4.0, will be employed to normalize and transform the data for univariate and multivariate statistical analysis (18). Additional statistical analysis may be performed using Graphpad Prism 8 (Graphpad Software, Inc)

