Biofluid and tissue microbiome analysis: DNA will be extracted from each blood, saliva and lung tumor tissue sample using the QIAamp® UCP Pathogen Mini Kit (Qiagen) with extended homogenization of the tissue samples using the Mini-Beadbeater-96 cell disrupter (Biospec Products). The quantity and quality of the DNA extracts will be determined using a DeNovix DS-11 FX+ Spectrophotometer/Fluorometer and Agilent 4200 TapeStation, respectively. The DNA will then be prepared for shotgun metagenomic sequencing using the Nextera® DNA Flex Library Preparation Kit (Illumina). DNA libraries will be normalized and quantified prior to pooling to ensure equal library representation. Pooled DNA libraries will then be sequenced using the Illumina NovaSeq 6000 S1 Reagent Kit and sequencer, generating 2 x 150 bp paired-end reads. Raw sequence reads (FASTQ files) will be imported into the Microbial Genomics Pro Suite within the CLC Genomics Workbench (version 11.0.1; <https://www.qiagenbioinformatics.com>) for QC, adapter trimming, and analysis. High-quality ($\geq Q30$) reads for each sample will be aligned to those in a blank extraction sample (negative control) that will be processed from DNA extraction through library preparation to identify and remove contaminating sequences. The filtered reads will then be aligned to a reference database consisting of complete genomes in the RefSeq database for prokaryotes (bacteria and archaea), eukaryotes (fungi and protozoa) and viruses for taxonomic profiling. The filtered reads will also be assembled into contigs *de novo*, and MetaGeneMark (20) will be used to identify protein-coding regions within the reads to predict functional diversity of the microbiota identified in the samples. The coding regions will be annotated with Pfam domains

Pilot Study: Metabolic and microbial profiling of lung cancer
Wake Forest Baptist Comprehensive Cancer Center (WFBCCC)
WFBCCC # 03219

and GO terms, and the abundance of functional categories will be estimated to build a functional profile for each sample.

The results from the taxonomic and functional profiling will each be merged to estimate similarities and differences among the samples. Heat maps will be generated using Euclidean distance and clustering based on average linkage to assess functional similarities between samples, and principal component analysis (PCA) ordination of Bray-Curtis similarity between samples will be used to visualize the microbiota diversity across the samples.

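### Section 6.3 takes change by 4 weeks after resection as the mark of a lung-cancer marker, but a single-group pre/post comparison cannot separate tumour removal from the operation and loss of lung

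*Combined protocol and SAP*

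**What the plan says.** Objective 2.2.1 (Section 2.2) is to assess metabolic and microbial signatures before and after surgery and "determine which are indicative of LC". Section 6.3 supplies the reasoning. It expects markers linked to the cancer to move once the tumour is out, and it adds the converse premise that "markers that are independent of lung cancer will not change between the two time points". From this it draws its first analysis, "a series of paired t-tests to determine which markers significantly change between the two time points for patients". Section 6.1 says the resulting effect sizes will be used, without multiplicity adjustment, to rank measures for future studies.

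The post-surgery sample is taken at the 4-week follow-up visit (Section 4.2.2). All patients are surgical candidates, and no comparison group is defined.

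Tumour tissue is obtained from the tumour bank and profiled under Section 4.2. For metabolomics, "Saliva, serum, urine and tissue aliquots will be prepared for analysis"; for metagenomics, "DNA will be extracted from each blood, saliva and lung tumor tissue sample". Section 5.2.1 lists four sets of measurements (metabolic and microbial, each pre- and post-surgery), with no tissue set. Section 6 does not mention tissue data.

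**The concern.** Read in reverse, the hypothesis makes change the criterion: a marker that changes is not independent of lung cancer. That holds only if nothing but tumour removal can move a marker between the two visits. Four weeks after a lung resection, healing and inflammation, peri-operative drugs, altered intake and activity, and reduced lung volume are all candidate causes. The plan gives reason to expect some of them. Objective 2.2.3 looks for signatures that depend on pulmonary function, and Section 4.2.1 treats medications, food and tobacco as possible confounders.

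At stake is the conclusion for objective 2.2.1 and the ranking passed to later studies. A marker moved only by the operation would be read as a lung-cancer signal and could be pursued as one. Tissue data that might help with interpretation are generated but given no part in that step.

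**Working it through.** **Inputs**
- Pairs: Section 6.1, "our target sample size of 90 patients (45 male/45 female) is the target for patients with both pre- and post- samples collected".
- Alpha and power: Section 6.1, "there is 80% power (using an alpha=0.05, 2-sided", for a difference of 0.30 SD.
- Size of a shift not due to the tumour: not in the documents. Assumed range: 0 to 0.5 SD of the paired difference.

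**Step 1: the plan's own figure.** Power of the paired t-test is P(|T| > critical value), with T noncentral t, df = 90 − 1 = 89 and noncentrality d√n.
- d√n = 0.30 × √90 = 0.30 × 9.487 = 2.846, which gives 80.4%.
- Normal approximation: Φ(2.846 − 1.960) = Φ(0.886) = 81.2%.
- Smallest difference detectable at 80% power: 0.299 SD.

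The stated 80% is reproduced if the SD is that of the paired difference. Section 6.1 speaks of the SD of the marker. Since SD(difference) = SD(marker) × √(2(1 − ρ)), the two agree at a pre/post correlation ρ of 0.5. On the raw-SD reading at other correlations:
- ρ = 0: d = 0.30/1.414 = 0.212, power 51%.
- ρ = 0.3: d = 0.30/1.183 = 0.254, power 66%.
- ρ = 0.7: d = 0.30/0.775 = 0.387, power 95%.

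**Step 2: what the test responds to.** Write the mean change as δ = δ(tumour) + δ(other), where δ(other) collects the operation, recovery, drugs and loss of lung. The paired t-test addresses δ = 0 and sees only the sum. For a marker with δ(tumour) = 0, the chance of being flagged depends on δ(other)/SD(difference) alone, through the same power function:

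| Assumed δ(other), SD of paired difference | Noncentrality | Probability flagged |
|---|---|---|
| 0 | 0 | 5% |
| 0.1 | 0.949 | 15.5% (16% rounded) |
| 0.2 | 1.897 | 47% |
| 0.3 | 2.846 | 80% |
| 0.4 | 3.795 | 96% |
| 0.5 | 4.743 | 99.7% |

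Noncentrality grows with √n, so more patients raise every probability below the first row.

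**Step 3: whether the plan separates the two parts elsewhere.**
- Comparison group: none.
- Covariates: of the confounders named in Section 4.2.1, only smoking history reappears in Section 6.3, as an exploratory characteristic. Extent of resection and peri-operative treatment do not appear.
- Lung function: Section 6.3 would use it at both time points, but the Section 4.3 schedule marks pulmonary function tests in the pre-surgery column only. As scheduled, its loss cannot be examined.
- Tissue: Section 4.2 sends tissue metabolomics through general univariate and multivariate processing, and merges microbiome profiles into heat maps and PCA. Neither is linked to pre/post change.

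**The case against.** The strongest reply is that this is a pilot. Section 6.3 words the premise as a hypothesis and the paired tests as a first analysis. Section 6.1 puts the results to use only as a ranking for later work. The Background speaks of potential markers, and outcome 5.2.1 asks neutrally what stays similar or changes. Medications, food and tobacco are recorded so that confounding can be recognised. The association of pre-surgery markers with stage, which the operation cannot have influenced, is already planned.

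Most of this is fair, and it limits the consequence. It does not remove the problem, because the ranking is the product of the pilot and confounding acts on the ranking itself. Objective 2.2.1 also asks for more than a neutral description of change.

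Three stronger readings are not supported:
- A reader might infer that the tissue data are never analysed. Section 4.2 does give them descriptive analyses; they are absent only from Sections 5 and 6.
- A reader might infer that the plan formally certifies each changed marker as a lung-cancer marker. It has no such step. The inference lies in the stated hypothesis and in the objective it serves.
- A reader might infer that surgery-driven markers will outrank tumour markers because every patient is operated on. Tumour resection is equally common to the group, so this does not follow.

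**Conclusion.** The concern holds as a fault in the stated inference, not in the arithmetic: the 80% power is correct for the SD of the paired difference. The paired test flags a cancer-independent marker as readily as a cancer marker with the same standardised shift, so change alone cannot show which signatures indicate lung cancer.

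The flagging probabilities of 16% to 99.7% rest on assumed shifts of 0.1 to 0.5 SD of the paired difference. That the operation moves markers at all is clinical reasoning, and the documents give neither the size of such shifts nor the share of markers affected. It would therefore be wrong to read 80% or 96% as the proportion of flagged markers that are false, or to claim that the premise has been shown to fail for every specimen type.

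The point should be addressed. It bears on objective 2.2.1 and the ranking, and leaves the primary feasibility outcome untouched.

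**What to change.** In Section 6.3, replace the hypothesis with: *markers that change after resection are associated with the tumour, the operation or both*. Report the paired-test results and the ranking as *post-resection change, origin undetermined*, not as indicative of lung cancer.

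Beside each changed marker, show two items as graded supporting evidence: the already planned association of its pre-surgery level with pathological stage and, where tissue is available, its tumour-tissue measurement. State this use of tissue in Sections 5.2 and 6.3.

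Neither item should serve as a qualifying rule, and the plan should say why:
- Detection in tissue is not tumour-specific. Section 4.2 lists amino acids, sugars, nucleotides and broad lipid classes among the analytes, and describes no normal tissue for comparison.
- A marker present equally across stages I to III will show no stage association. Without multiplicity adjustment, about 5% of markers unrelated to stage will show one by chance at the 0.05 level.

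No new patients, visits or assays are needed. The cost is rewording, a small amount of extra tabulation, and a note on how missing tissue is shown, since it comes through a separate bank protocol. The downside is a weaker headline for objective 2.2.1.

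### 6.1 waives multiplicity adjustment because effect sizes will be ranked, but 6.3 specifies no ranking and classifies markers by unadjusted paired t-tests

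*Combined protocol and SAP*

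**What the plan says.** Section 6.1 (Sample Size and Power) gives a power statement for one marker compared before and after surgery within patients: 90 patients, two-sided alpha 0.05, 80% power for a difference of 0.30 SD. It then says: "Multiple comparison adjustments are not considered at this time since the focus of examining these effect size estimates is to determine an overall ranking". The stated use of that ranking is "in order to inform future studies concerning which signatures may be most promising to examine further".

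Section 6.3 (Analysis of Secondary Outcomes) sets out the marker analyses:

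- **Before versus after surgery.** The hypothesis is that "markers that are associated with lung cancer will change between the pre- and post- surgery setting", and that markers unrelated to lung cancer will not. From this follows, as the first analysis, "a series of paired t-tests to determine which markers significantly change between the two time points for patients".
- **Stage.** A linear model per marker asks whether "pre-surgery, post-surgery or change from pre- to post-surgery metabolic or microbial measures are different depending on LC Stage", that is, whether stage "is associated with any marker".
- **Pulmonary function.** "we will use the same approach as for LC Stage", with pulmonary function as a continuous variable, so that associations can be examined.
- **Clusters.** For these the plan adds: "therefore these cluster analyses will be considered exploratory and hypothesis generating". A similar label closes the section, after the paragraph on additional patient-level characteristics.

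Section 6.3 names no effect-size statistic, ordering rule, interval, alpha or multiplicity procedure for the individual markers.

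**The concern.** The waiver in 6.1 rests on one reason: the output is a ranking. A ranking by effect size can be read without a significance threshold, so declining adjustment is coherent there. The paired analysis in 6.3 does something else. It sorts markers into changed and not changed by a significance test, and the hypothesis stated just before gives that label a meaning, namely a link with lung cancer. The reason in 6.1 does not reach a classification of that kind.

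Followed as written, 6.3 would hand later studies a list of significant markers. Its readers could not tell how much of the list is chance, and the plan's own hypothesis would invite them to treat each entry as related to the disease.

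**Working it through.** **Inputs.** From 6.1: 90 pairs, two-sided alpha 0.05, 0.30 SD, 80% power. Section 6.3 states no alpha, so 0.05 is carried over. Section 4.2.2 (Data generation) gives a potential of hundreds to thousands of metabolites per sample but no fixed count; 100 and 1000 are used here as an assumed range. Counts scale in proportion to the number of markers. The shares of truly changed markers (5, 10, 20%) are assumptions.

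**Step 1: the plan's own figure.** Paired t-test, 89 degrees of freedom, noncentrality 0.30 × √90 = 2.85, two-sided 0.05: power 80.4%. The stated 80% reproduces, taking the SD as that of the paired difference. It holds for a single marker at unadjusted 0.05.

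**Step 2: no marker changes.** Expected false calls = 0.05 × number of markers.

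- 100 markers: 0.05 × 100 = 5.
- 1000 markers: 0.05 × 1000 = 50.

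These expectations do not depend on correlation between markers.

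**Step 3: some markers change by 0.30 SD.** For 1000 markers with true share π, false calls = 0.05 × (1 − π) × 1000 and true calls = 0.8038 × π × 1000.

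| True share (assumed) | False calls | True calls | False share of the list |
|---|---|---|---|
| 5% | 47.5 | 40.2 | 47.5 / 87.7 = 54% |
| 10% | 45.0 | 80.4 | 45.0 / 125.4 = 36% |
| 20% | 40.0 | 160.8 | 40.0 / 200.8 = 20% |

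The shares are the same for 100 markers.

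**Step 4: would a bare ranking be enough?** In simulation with 90 pairs and 1000 independent markers, none of which changes, the largest observed standardized change averages 0.38 (5th to 95th percentile 0.32 to 0.45). That exceeds the 0.30 SD for which 6.1 is powered. The top of a ranking can therefore look impressive by chance alone, and a q-value beside each entry shows this at little cost.

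**Step 5: why the q-value family must be stated.** With all 1000 markers null and a 10% Benjamini-Hochberg threshold used as an example, simulation gives at least one false call in about 10% of studies if the markers form one family, and in about 65% if they are split into ten independent families of 100. A q-value cannot be interpreted without knowing its family.

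**The case against.** The strongest reply is that multiplicity was not overlooked. Section 6.1 raises it, declines adjustment, gives a reason and states the use. The waiver closely follows the before-and-after power calculation, which is the comparison that the paired t-tests carry out, and the document calls itself a pilot with many exploratory objectives. Moreover, the paired t statistic divided by √n is the standardized paired change. With equal numbers of pairs, ordering markers by t gives the promised ranking. In a simulation of 1000 markers with true changes of 0.30 SD, the top 20 by absolute t are about 91, 99 and 100% true at true shares of 5, 10 and 20%, so a ranking can serve the stated purpose.

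Much of this stands. It shows that the remedy is small and that strict familywise control is not called for: Bonferroni would cut power at 0.30 SD from 80% to 23% with 100 markers and to 9% with 1000. It does not remove the mismatch, because 6.3 asks for a significance classification and never for the ordering.

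Three stronger readings are tempting, and the documents do not support them.

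- *Every per-marker analysis is an unadjusted significance decision.* One paired test plus three stage and three pulmonary-function tests makes seven per marker, hence 7 × 0.05 = 0.35 flags per null marker, or 35 per 100 and 350 per 1000. But significance is named as the criterion only for the paired tests. The other two analyses examine associations and set no decision rule or alpha. The total also counts flags, not distinct markers.
- *The paired tests are meant as confirmatory.* The exploratory labels within 6.3 attach most directly to the cluster and patient-characteristic analyses, but the general framing in 6.1 softens the whole plan, and the closing sentence of 6.3 could be read more widely.
- *A q-value cut-off is needed.* At 5% true and 0.30 SD, a 10% Benjamini-Hochberg cut-off in one family of 1000 would reduce the true markers called from 40.2 to 19.2. That is a debatable trade in a discovery pilot, and nothing in the plan requires it.

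**Conclusion.** The point holds as an inconsistency between 6.1 and 6.3, explicit for the paired t-tests and only implied for stage and pulmonary function. That finding rests on the text alone. The 5 to 50 chance calls rest on 6.1's alpha being the one applied and on the assumed 100 to 1000 markers. The 54, 36 and 20% false shares rest further on the assumed true shares and on a uniform true change of 0.30 SD; they illustrate the problem and do not predict the result. The power figure in 6.1 is not in error. The consequence is confined to how secondary marker results are reported and interpreted, and correcting it is a worthwhile, inexpensive improvement.

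**What to change.** In 6.3, replace the classification of markers by significant change with wording such as:

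> Markers will be ranked by standardized paired change (mean change divided by the SD of change) with 95% CI. Unadjusted p-values and Benjamini-Hochberg q-values, with the family stated, will be shown beside the ranking. Marker associations with LC stage and pulmonary function will be reported in the same way. All per-marker analyses are exploratory, and a marker's place in the ranking is not by itself evidence of association with lung cancer.

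No q-value cut-off is needed. The rationale in 6.1 can then stay, because the analysis would match it.

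The cost is one extra output column and giving up a list of significant markers. Every marker stays visible with its effect size and unadjusted p-value. Sample size, sample collections and the primary feasibility analysis are unchanged.
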